8.8.9. Records of investigation discontinuation

For patients who withdraw from the investigation during the observation period, enter the date of discontinuation. For the main reason for discontinuation, i.e., why the investigation cannot be continued, select one of the following options.

(Not making another visit, death, transfer to another hospital or department, or other)

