## 6. ENDPOINTS AND COVARIATES

### 6.1. Safety Endpoints

- Adverse events: All undesirable or unintended signs or symptoms that occurred after administration of this drug, regardless of causal relationship
- Adverse drug reactions: Adverse events assessed as causally related to this drug by the physician

- Serious adverse events or serious adverse drug reactions: Adverse events or adverse drug reactions assessed as serious by the physician

- Death after HSCT:

- Time to death after HSCT: Days and weeks from the date of first HSCT after the start of this drug to the date of death
- Event: Death (for any cause)
- Censoring: The patient is confirmed alive at the time of completion or discontinuation of the survey. The endpoint will be censored on the day when patient's survival was last confirmed.

Early death after HSCT is defined as the above event that occurred within 100 days after the first HSCT after the start of this drug. Early death is supposed to be absent if the patient died on 101 days or later, or was confirmed alive at the time of completion/discontinuation of the survey.

- Transplant-related death after HSCT (non-relapse death):

- Time to transplant-related death after HSCT: Days and weeks from the date of first HSCT after the start of this drug to the date of death.
- Event: Death due to non-tumor-related causes, resulting from worsening of the target disease of this drug
- Competing risks: Death due to tumor-related causes, resulting from worsening of the target disease of this drug
- Censoring: The patient is confirmed alive at the time of completion or discontinuation of the survey. The endpoint will be censored on the day when patient's survival was last confirmed.

Early transplant-related death after HSCT (non-relapse death) is defined as the above event that occurred within 100 days after the first HSCT after the start of this drug. Early death is supposed to be absent if the patient died on 101 days or later, or was confirmed alive at the time of completion/discontinuation of the survey.

- Transplant-unrelated death after HSCT (relapse death):

- Time to transplant-unrelated death after HSCT: Days and weeks from the date of first HSCT after the start of this drug to the date of death.
- Event: Death due to tumor-related causes, resulting from worsening of the target disease of this drug
- Competing risks: Death due to non-tumor-related causes, resulting from worsening of the target disease of this drug

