#### 8.1.4. Time-to-event data

For time-to-event data, the median, 1st quartile, and 3rd quartile will be determined using the Kaplan-Meier method. The rate at each time point will also be determined. To estimate CIs, log-log transformation will be used (this corresponds to specifying loglog under the conftype option in the proc lifetest statement of the SAS® lifetest procedure). In addition, Kaplan-Meier plots will be presented.

When time data are compared between subgroups using the Kaplan-Meier method, the hazard ratio of event occurrence and its 95% CI will be determined using the Cox proportional hazards model (ties handled by the Breslow method). In addition, the hazard ratio and its 95% CI will be presented graphically.

In the analysis of time data with competing risks, the cumulative incidence rate at each time point that takes into account competing risks will be determined (this corresponds to using the event code option in the time statement of the SAS® lifetime procedure). The standard error is to be estimated by the delta method. In addition, the time course of cumulative incidence will be graphically presented.

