For ADRs that occurred in at least 10% of patients, number and proportion of patients with the ADRs will be summarized for each SOC and PT by category of timing of initial onset [ $< 4$  weeks after the start of treatment,  $\geq 4$  weeks to  $< 8$  weeks,  $\geq 8$  weeks to  $< 12$  weeks,  $\geq 12$  weeks to  $< 16$  weeks,  $\geq 16$  weeks to  $< 20$  weeks,  $\geq 20$  weeks to  $< 24$  weeks,  $\geq 24$  weeks].

In addition, time to event will be summarized as per Section 8.1.4 with event being the first onset of the AR. The analysis will be performed with the following specifications:

- Analysis set: SAS
- Handling of patients with no AR: Censored at 28 days after the final dose of this drug.
- Time points for rate estimation: Weeks 1, 2, 3, 4, 8, 12, 16, 20, and 24
- **Occurrence of adverse drug reactions by inclusion/exclusion in the safety analysis set**

For the population of patients whose case report form was collected, a listing of ADRs in patients excluded from the SAS will be prepared. In addition, excluded patients with ADRs will be summarized by SOC and PT.

- **VOD/SOS**

Events of VOD/SOS reported as AR will be analyzed. Events included in each analysis will not be limited to events of initial onset. Unless otherwise specified, VOD/SOS events will be summarized respectively for each of the following categories.

- VOD/SOS that occurred after the start of this drug (Use the SAS as the analysis set.)
- VOD/SOS that occurred with absence of HSCT after the start of this drug (Same as above): Here, "absence of HSCT" means that VOD/SOS occurred with no HSCT or occurred before any HSCT.
- VOD/SOS that occurred with presence of HSCT after the start of this drug (Patients in the SAS who underwent HSCT after the start of this drug will be analyzed)

**Occurrence of VOD/SOS:** The number of patients with VOD/SOS and its proportion will be summarized. Among the factors listed in "Details of adverse drug reactions" in Section 8.2.3.1, n and proportion will be summarized with respect to each of the following factors: Action taken [discontinuation, temporary suspension or dose reduction, none], Outcome [fatal, not recovered, recovered with sequelae, recovering, resolved/recovered, unknown], CTCAE Grade (1) [1, 2, 3, 4, 5, unknown], and CTCAE Grade (2) [ $< 3$ ,  $\geq 3$ , unknown].

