**Timing of onset of VOD/SOS:** To analyze the timing of onset of VOD/SOS, summary statistics will be performed as per Section 8.1.1, for the following kinds of time.

- Time from the final dose of this drug: Time (weeks) from the final dose of this drug to the onset of VOD/SOS
- Time from HSCT: Time (weeks) from the first HSCT after the start of this drug to the onset of VOD/SOS. Only VOD/SOS events that occurred with presence of HSCT after the start of this drug will be included in this analysis (Similar limitation shall also apply to the analysis set).

Patients with VOD/SOS will be counted by each of the following timing factors. For each timing factor, data will also be summarized in a histogram (The longitudinal axis is frequency. The width of each onset period will depend on the actual duration of the period).

- Time from the final dose of this drug: < 2 weeks, ≥ 2 weeks to < 4 weeks, ≥ 4 weeks to < 8 weeks, ≥ 8 weeks to < 12 weeks, ≥ 12 weeks to < 16 weeks, ≥ 16 weeks
- Time from HSCT 1: < 2 weeks, ≥ 2 weeks to < 4 weeks, ≥ 4 weeks to < 6 weeks, ≥ 6 weeks to < 8 weeks, ≥ 8 weeks. This time is defined as the time starting from the first HSCT after the start of this drug.
- Time from HSCT 2: ≤ 3 weeks, > 3 weeks. This time is defined as the time starting from the first HSCT after the start of this drug.

Regarding the timing of onset of events described in "Timing of onset of adverse drug reactions" in Section 8.2.3.1, data will be analyzed with the following specifications.

- Analysis set: Patients who finished the survey (Patients who are recorded as discontinued in the "Record of continued/discontinued survey [treatment period]" in the case report form or patients for whom "Record of continued/discontinued survey [follow-up period]" in case report form is filled in. The latter means the survey is discontinued and completed for the patient.)
- Handling of patients who did not experience ADRs: If the survey had been discontinued for the patient, data shall be censored on the date of discontinuation based on the "Record of continued/discontinued survey" in the case report form; if the survey had been completed for the patient, data shall be censored on the last observation date defined in Section 7.
- Time points for rate estimation: Every 4 weeks from Week 4 to Week 52

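### The Week 4–52 VOD/SOS onset rates use Kaplan-Meier with deaths censored, so they exceed the cumulative incidence of VOD/SOS adverse drug reactions whenever deaths without VOD/SOS precede later onsets

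*SAP*

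**What the plan says.** The plan for this output is spread over several sections.

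- **Event.** SAP 8.2.3.1 (VOD/SOS) restricts the event to adverse drug reactions: "Events of VOD/SOS reported as AR will be analyzed".
- **Routing.** The VOD/SOS timing paragraph applies the onset analysis defined earlier in 8.2.3.1, in which "time to event will be summarized as per Section 8.1.4 with event being the first onset of the AR".
- **Estimator.** In SAP 8.1.4, "the median, 1st quartile, and 3rd quartile will be determined using the Kaplan-Meier method". The same paragraph covers the rate at each time point.
- **Time points.** For VOD/SOS: "Time points for rate estimation: Every 4 weeks from Week 4 to Week 52".
- **Censoring.** "If the survey had been discontinued for the patient, data shall be censored on the date of discontinuation". If the survey was completed, the patient is censored on the last observation date defined in SAP 7.
- **Reasons for discontinuation.** Protocol 8.8.9 offers: "Not making another visit, death, transfer to another hospital or department, or other".
- **Competing risks.** SAP 8.1.4 also has a method for data with competing risks, under which "the cumulative incidence rate at each time point that takes into account competing risks will be determined". SAP 6.1 names such risks only for the two cause-specific endpoints of death after HSCT, for example "Competing risks: Death due to tumor-related causes, resulting from worsening of the target disease of this drug". SAP 8.2.3.3 applies the method to mortality after HSCT. Neither document names death as a competing event for VOD/SOS onset.

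**The concern.** A patient who has died cannot develop VOD/SOS. Kaplan-Meier treats a censored patient as still at risk, with the same future hazard as those who remain under observation. Censoring at death therefore passes the deceased patients' share of risk to the survivors. The result describes onset in a population where nobody dies, not the proportion of treated patients who have had a VOD/SOS reaction by a given week.

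The SAP anticipates deaths in this window: it plans survival rates from Month 3 (8.2.4.4) and mortality after HSCT from Week 4 (8.2.3.3). VOD/SOS belongs to the first important identified risk in Protocol 7.1.1 and is the event behind the sample size in Protocol 8.10.2. Without a named competing event or a label, the Week 4–52 rates are likely to be read as proportions of patients affected, which they are not.

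The upward direction is claimed only against the cumulative incidence of VOD/SOS adverse drug reactions. Nothing is claimed about all VOD/SOS, because events judged unrelated to the drug are not counted.

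**Working it through.** **1. What happens to a death without VOD/SOS.** If it is recorded as a discontinuation, the patient is censored at the discontinuation date. If it is recorded under completion, the patient is censored at the last observation date. Both routes lead to censoring.

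**2. The plan's own figures.** The documents state no figure for the onset rates. The related figure, 80.4% power with 176 patients, reproduces: 88 per group, 18.5% against 6.2%, two-sided 0.1, pooled variance, gives 80.2%. It concerns a comparison of proportions and is unaffected.

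**3. Hand example of the mechanism.** Take 176 patients: 11 onsets, then 53 deaths without VOD/SOS (30%), then 11 more onsets.
- Cumulative incidence = 22/176 = 12.5%.
- At risk after the first onsets: 176 − 11 = 165. After the deaths: 165 − 53 = 112. After the last onsets: 112 − 11 = 101.
- 1−KM = 1 − (165/176) × (101/112) = 1 − 0.9375 × 0.9018 = 15.5%.
- With no death before the last onset, both are 12.5%.

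**4. Size over an assumed range.** Inputs: Week 52 cumulative incidence fixed at 12.3% (26/212, Protocol 8.10.2, borrowed as a 52-week value); net 52-week mortality m (assumed); onset at a constant rate over weeks 0 to T and none after (assumed).
- Death hazard: d = −ln(1−m)/52 per week.
- VOD/SOS hazard h on [0, T], solved from h/(h+d) × [1 − exp(−(h+d)T)] = 0.123.
- 1−KM at week t = 1 − exp(−h × min(t, T)).

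Example with m = 0.50, T = 52: d = 0.01333, h = 0.003554, so 1−KM at Week 52 = 1 − exp(−0.1848) = 16.9%.

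1−KM at Week 52, against a true 12.3%:

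| Net 52-week mortality | T = 16 | T = 26 | T = 52 |
|---|---|---|---|
| 10% | 12.5% | 12.6% | 12.9% |
| 30% | 13.0% | 13.4% | 14.6% |
| 50% | 13.6% | 14.5% | 16.9% |
| 70% | 14.7% | 16.2% | 20.7% |

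At Week 24 with m = 0.50, 1−KM reads 13.6% against 12.3% (T = 16), or 8.2% against 7.0% (T = 52).

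**5. Cross-checks.** A simulation of 400,000 patients gave 16.9% against 12.3% (m = 0.50, T = 52) and 13.7% against 12.3% (m = 0.50, T = 16). A second parameterisation fixed the proportion who die without VOD/SOS by Week 52, with both hazards constant. It gave 13.0% at 10% such deaths, 14.8% at 30% and 19.6% at 60%. A discrete dataset of 176 patients with 22 onsets and 70 deaths has a cumulative incidence of 12.5%. Its 1−KM was 16.3% with onsets and deaths interleaved over the year, 14.4% with onsets in Weeks 4–30, and 12.5% with all onsets before any death.

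**The case against.** The strongest reply is that the SAP never calls these rates a cumulative incidence. The paragraph concerns timing of onset, and Kaplan-Meier with death censored is a recognised net summary. On that view the defect is an undeclared target rather than a wrong calculation. This is fair as far as it goes, but it still calls for a label, because an unlabelled rate at Week 52 will be set beside the crude proportion and read the same way.

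Second, the crude number and proportion with VOD/SOS, the onset-interval counts and the individual patient graphs are all reported, testing is exploratory (SAP 4.1) and there are no decision rules (SAP 4.2). This stands and limits the consequence to one descriptive output. It does not supply a rate over Weeks 4–52 that handles both loss to follow-up and death.

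Third, the upper figures need high mortality and onset spread evenly over a year, which the documents do not support. With onset confined to 8 weeks the excess is only 0.1, 0.3 and 0.65 points at 10%, 30% and 50% mortality. For scale, the exact 95% confidence interval for 22/176 is 8.0–18.3%. The 12.3% is also a crude clinical-study incidence, not stated to be a 52-week or reaction-only figure. The hand example, with all its deaths between two blocks of onsets, shows the mechanism and is not a forecast. All of this stands: the size is unknown and may be small.

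Fourth, if the curve is also drawn for VOD/SOS without or before HSCT and for VOD/SOS after HSCT, naming death does not settle how HSCT itself or the time origin is handled. That is a separate clarification; death needs handling in every category regardless.

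**Conclusion.** The concern holds. Followed as written, the SAP censors deaths without VOD/SOS, and its Week 4–52 rates exceed the cumulative incidence of VOD/SOS adverse drug reactions whenever such deaths precede later onsets.

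The direction follows from the documents; the size does not. Under the constant-hazard assumptions above, the Week 52 excess is:

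- +0.2 to +0.6 points at 10% net mortality
- +0.7 to +2.3 points at 30%
- +1.3 to +4.6 points at 50%
- +2.4 to +8.4 points at 70%

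The lower ends assume onset within 16 weeks and the upper ends onset spread over 52 weeks. Earlier onset makes the excess smaller, and it is zero if all onsets precede all deaths. The point should be fixed, but it reaches only the timing-of-onset output.

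**What to change.** In the timing-of-onset paragraph for VOD/SOS in SAP 8.2.3.1, name death without VOD/SOS as a competing event and report the Week 4–52 rates by the cumulative incidence method of SAP 8.1.4. Keep censoring for patients alive at discontinuation or completion. If the Kaplan-Meier curve is retained, label it as a net (cause-specific) estimate.

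If the output is produced by HSCT category, state there how HSCT and the time origin are treated.

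The cost is a wording change in one SAP section and one changed output, repeated for any HSCT categories shown. The method is already specified, and the date of death is already collected (Protocol 8.8.12), so no new data are needed.

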8.7. Observation Period

Observation period: The observation period will be 52 weeks for patients not undergoing HSCT within 52 weeks after the start of BESPONSA treatment or until 52 weeks following HSCT for patients undergoing it within 52 weeks after the start of BESPONSA treatment. For a patient starting BESPONSA treatment before 30 April 2020 who is transferred to another hospital during the observation period, the conclusion of the agreement on the implementation of this investigation should be requested to the hospital to which the patient has been transferred, and data from there should be collected to the extent possible.

(1) Treatment phase

From treatment initiation to Day 28 post-treatment: Safety (e.g., AEs) and efficacy (hematologic remission and survival)

(2) Follow-up phase

From Day 29 post-treatment to Week 52 (patients who did not undergo HSCT before Week 52) or 52 weeks after HSCT (patients who underwent HSCT before Week 52): Safety (VOD/SOS) and efficacy (survival)

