## 2.1. Study Design

- **Target population**

*All patients who received this drug will be included in this survey.*

- **Survey period**

*The scheduled periods of this survey are as follows:*

*Survey period: From the date of launch of this drug to 5 years\**

*Registration period: From the date of launch of this drug to the time of lifting of approval conditions for all-case survey\**

*\*: Patients who started to receive this drug on or after May 1, 2020 will only be registered.*

The protocol may be changed to terminate the registration only period, but this change will not affect the SAP.

- **Observation period**

*Observation period: The observation period is to be 52 weeks for patients who did not undergo hematopoietic stem cell transplant (HSCT) within 52 weeks after the start of the treatment with this drug and up to 52 weeks after HSCT for patients who underwent HSCT within 52 weeks after the start of this drug. If patients who started to receive this drug on or before April 30, 2020 are transferred to another hospital during the observation period, the transferred hospitals will be requested to conclude a contract for the conduct of this survey, and the information at the transferred hospitals will be collected as much as possible.*

*[1] Treatment Period*

*From the start of treatment to Day 28 post-final dose: For assessments of safety (e.g., adverse events) and effectiveness (hematologic response, survival time)*

*[2] Follow-up period*

*For 52 weeks from 29 days after the final dose (for patients who did not undergo HSCT by 52 weeks after the start of treatment) or for 52 weeks after HSCT (for patients who underwent HSCT by 52 weeks after the start of treatment): For assessments of safety (VOD/SOS) and effectiveness (survival time)*

The starting point for the 52 week follow-up after HSCT is the day of the last HSCT performed within 52 weeks after the start of this drug.

- **Safety specification**

See Protocol Section 7.1.

- **Sample size and its rationale**

*Of the patients who have received this drug, a total of 176 patients with relapsed or refractory CD22 positive (CD22+) acute lymphocytic leukemia (ALL) will be included in the safety analysis set. In consideration of dropouts during the survey, 200 patients will be registered.*

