- White blood cell count immediately before the start of this drug [ $\leq 4000/\text{mm}^3$ ,  $\geq 4000/\text{mm}^3$ , not performed]
- Neutrophil count immediately before the start of this drug [ $\leq 2000/\text{mm}^3$ ,  $\geq 2000/\text{mm}^3$ , not performed]
- Platelet count immediately before the start of this drug [ $< 10 \times 10^4/\mu\text{L}$ ,  $\geq 10 \times 10^4/\mu\text{L}$ , not performed]
- Peripheral blast count immediately before the start of this drug [ $\leq 1000/\mu\text{L}$ ,  $> 1000/\mu\text{L}$ , not performed]
- Myeloblast count immediately before the start of this drug [ $\leq 50\%$ ,  $> 50\%$ , not performed]
- Salvage line of the induction treatment with this drug [Initial induction, 1st, 2nd, 3rd or later]
- HSCT before the start of this drug [not performed, performed]

Subgroup analyses of safety will be performed also for the following factors:

- HSCT after the start of this drug [not performed, performed]
- Type of the first HSCT after the start of this drug [autologous transplant, allogeneic hematopoietic stem cell transplant with myeloablative conditioning, allogeneic hematopoietic stem cell transplant with nonmyeloablative conditioning, unknown]
- Donor of the first HSCT after the start of this drug [alternative donor, matched related donor]
- Conditioning with alkylating agent for the first HSCT after the start of this drug [ $\leq 1$  agent (including no conditioning),  $\geq 2$  agents]
- Conditioning with busulfan for the first HSCT after the start of this drug [not performed (including no conditioning), performed]
- ECOG PS before conditioning for the first HSCT after the start of this drug [0, 1,  $\geq 2$ , not performed]
- AST and ALT levels before conditioning for the first HSCT after the start of this drug [ $\leq 1.5 \times$  the institutional upper limit of normal range (IULN), either  $> 1.5 \times$  IULN, not performed]
- $\gamma$ -GTP level before conditioning for the first HSCT after the start of this drug [ $\leq 50$  IU/L,  $> 50$  IU/L, not performed]

- Total bilirubin level before conditioning for the first HSCT after the start of this drug [≤ institutional upper limit of normal range (IULN), > IULN, not performed]
- Hemoglobin level before conditioning for the first HSCT after the start of this drug [< 10 g/dL, ≥ 10 g/dL, not performed]
- Platelet count before conditioning for the first HSCT after the start of this drug [< 10 × 10^4/µL, ≥ 10 × 10^4/µL, not performed]

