#### 8.1.3. Binary variables

For binary variables, patients falling into each binary category will be summarized in terms of frequency (n) and proportion. If a confidence interval (CI) is determined for a proportion, the two-sided 95% CI will be determined using the exact method.

For a comparison of proportion between subgroups, the risk ratio (RR) and its 95% CI will be determined. In addition, the RRs and their 95% CIs will be graphically presented.

For statistical tests, Fisher's exact test will be performed to test correlations in nominal scale data, and Cochran-Armitage test (exact method) to test correlations in ordinal scale data. If, however, it is difficult to use the exact method, chi-square test or Cochran-Armitage test with normal approximation will be used as an alternative to the exact method.

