### **8.2.3. Safety analyses**

Adverse drug reactions (ADRs) and adverse events (AEs) that occurred in the following periods will be collected for summary: for ADRs and AEs other than VOD/SOS, those that occurred from the start of this drug to 28 days after the final dose of this drug will be collected; for ADRs and AEs of VOD/SOS in patients who did not undergo HSCT within 52 weeks after the start of this drug, those that occurred within 52 weeks after the start of this drug will be collected; for ADRs and AEs of VOD/SOS in patients who underwent HSCT within 52 weeks after the start of this drug, those that occurred within 52 weeks after the last HSCT will be collected. The listings will include all events reported in this survey.

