**Exploration of factors associated with the occurrence of VOD/SOS (subgroup analyses):** Patients who experienced VOD/SOS after the start of this drug and patients who experienced VOD/SOS with HSCT performed after the start of this drug will be summarized in terms of n and proportion by each of the following factors selected from those specified in Section 5.4. In addition, risk ratios for the proportion of patients with the AR for different subgroups will be determined as per Section 8.1.3 and presented graphically. If, however, there is a category with less than 10 patients and after reconsideration it is considered difficult to determine the risk ratio for the category, it will not be determined for the relevant category. To investigate correlation between factors and occurrence of the ADR, statistical tests specified in Section 8.1.3 will be performed.

- Age [ $< 15$  years,  $\geq 15$  to  $< 65$  years,  $\geq 65$  years]
- Age [ $< 18$  years,  $\geq 18$  to  $< 55$  years,  $\geq 55$  years]
- Age [ $< 15$  years,  $\geq 15$  to  $< 40$  years,  $\geq 40$  years]
- Hepatic impairment
- Medical history (past) - VOD/SOS
- Medical history (past) - Hepatitis or hepatic disease
- Medical history (present) - VOD/SOS
- Medical history (present) - Hepatitis or hepatic disease
- ECOG PS before the start of this drug [ $0, 1, \geq 2$ , not performed]
- AST and ALT levels immediately before the start of this drug
- $\gamma$ -GTP level immediately before the start of this drug
- Total bilirubin level immediately before the start of this drug
- Platelet count immediately before the start of this drug
- Peripheral blast count immediately before the start of this drug
- Salvage line of the induction treatment with this drug
- HSCT before the start of this drug
- HSCT after the start of this drug

Similarly, VOD/SOS that occurred with HSCT performed after the start of this drug will be analyzed with respect to the following factors:

- Type of the first HSCT after the start of this drug
- Donor of the first HSCT after the start of this drug
- Conditioning with alkylating agent for the first HSCT after the start of this drug
- Conditioning with busulfan for the first HSCT after the start of this drug

- ECOG PS before conditioning for the first HSCT after the start of this drug [0, 1, ≥ 2, not performed]
- AST and ALT levels before conditioning for the first HSCT after the start of this drug

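### The VOD/SOS risk ratio for HSCT after drug start uses an untimed ever/never split with unequal observation windows, so it cannot be read even as an association of HSCT with later VOD/SOS

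*SAP*

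**What the plan says.** SAP 8.2.3.1, under the exploration of factors associated with VOD/SOS, takes as its outcomes "Patients who experienced VOD/SOS after the start of this drug and patients who experienced VOD/SOS with HSCT performed after the start of this drug". For each listed factor it plans counts, proportions, a risk ratio, a graph and a test. HSCT after drug start is on the list. SAP 5.4 gives it two levels and no timing: "HSCT after the start of this drug [not performed, performed". The measure comes from SAP 8.1.3: "For a comparison of proportion between subgroups, the risk ratio (RR) and its 95% CI will be determined", with Fisher's exact test for nominal data.

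The counting windows are in SAP 8.2.3. For patients without HSCT in the first 52 weeks, VOD/SOS events are "those that occurred within 52 weeks after the start of this drug will be collected"; for recipients they are "those that occurred within 52 weeks after the last HSCT will be collected". SAP 2.1 starts the post-HSCT period at "the day of the last HSCT performed within 52 weeks after the start of this drug". Protocol 8.7 likewise observes recipients "until 52 weeks following HSCT for patients undergoing it within 52 weeks after the start of BESPONSA treatment". Protocol 8.8.14 records VOD/SOS from the start of treatment, so events before HSCT are in the data.

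Elsewhere in 8.2.3.1 the SAP does respect order. Its category for absence of HSCT "means that VOD/SOS occurred with no HSCT or occurred before any HSCT"; the onset summaries measure time from first HSCT; the table on performance of HSCT separates events before or without HSCT from events after it; and individual graphs show each case's dates.

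**The concern.** For this factor, the exposure group is fixed by something that may happen after the outcome. Three features follow from the text alone.

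- **Order.** VOD/SOS at Week 6 followed by HSCT at Week 14 is a case under performed, although no HSCT had taken place when it occurred. A patient with VOD/SOS at Week 6 and no later HSCT is a case under not performed, whatever the reason HSCT did not follow.
- **Survival to HSCT.** A patient can enter the performed group only by living to HSCT. Early deaths, with little time to develop VOD/SOS, all fall under not performed.
- **Window.** Recipients contribute from more than 52 up to about 104 weeks from drug start (52 + 52). Others contribute at most 52.

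SAP 6.4 names HSCT status as a potential VOD/SOS risk factor, and evaluating such factors is the stated basis of the sample size (Protocol 8.10.2). The ratio would appear on a graph beside factors fixed at baseline, with nothing to tell the reader that it is built differently. SAP 8.2.4.4 and 8.2.4.5 warn that observation differs by HSCT status, but only for overall survival.

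**Working it through.** **The plan's own figure.** Protocol 8.10.2 assumes overall incidence 12.3%, relative risk 3.0, a 1:1 split, 176 patients and two-sided alpha 0.1. The group rates sum to 2 × 12.3% = 24.6%, so the low rate is 24.6/4 = 6.15% and the high rate 18.45%. With 88 per group:
- pooled SE = √(2 × 0.123 × 0.877/88) = 0.0495
- unpooled SE = √((0.1845 × 0.8155 + 0.0615 × 0.9385)/88) = 0.0486
- z = (0.123 − 1.645 × 0.0495)/0.0486 ≈ 0.85, power about 80.4%.

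The stated 80.4% reproduces (80.2% with the rounded 18.5% and 6.2%). It does not depend on the present point.

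**Does any planned analysis compare by HSCT status and respect order?**
- The second outcome, VOD/SOS with HSCT performed, is limited to recipients. It has no not-performed group and gives no ratio for this factor.
- The performance-of-HSCT table gives counts and proportions by order, with no ratio and no time at risk.
- The time-to-event analysis of onset gives rates every 4 weeks to Week 52, with no stated comparison by HSCT.
- No landmark, time-dependent or person-time comparison for VOD/SOS is specified.

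**Longer window alone.** Assume a constant hazard giving 12.3% at 52 weeks, no deaths and no HSCT effect: λ = −ln(1 − 0.123)/52 = 0.002524 per week. For HSCT at week t, the ratio is [1 − exp(−λ(t + 52))]/0.123.

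| HSCT at week | Risk in recipients | Ratio (truth 1.0) |
|---|---|---|
| 4 | 0.132 | 1.07 |
| 12 | 0.149 | 1.21 |
| 24 | 0.175 | 1.42 |
| 52 | 0.231 | 1.88 |

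**All three features together, no HSCT effect.** The documents supply none of the inputs, so all are assumed: VOD/SOS risk 15% in the absence of death (by Week 52 if constant, or all within the first 16 or 24 weeks); half of patients eligible for HSCT, at a time uniform over Weeks 8-24; exponential death with median 26-40 weeks without HSCT and 26-100 weeks after it; observation to Week 52 or HSCT + 52 weeks; 2 million patients per scenario.

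| VOD/SOS hazard | VOD/SOS never prevents HSCT | VOD/SOS always prevents HSCT |
|---|---|---|
| Constant | about 1.5-2.5 | about 0.7-1.4 |
| First 16-24 weeks only | about 1.2-1.5 | about 0.1-0.4 |

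A second constant-hazard set (12.3% at 52 weeks, 45% planned for HSCT at a mean of about 13 weeks, 52-week mortality 0-65%, 0-100% of patients with pre-HSCT VOD/SOS losing their HSCT) gave 0.84-1.56 under no effect. With a true hazard ratio of 3 and mortality of 0% or 50%, it gave 2.24-3.25.

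**Check on the remedy.** Under a constant hazard, a rate ratio with HSCT status switching on the HSCT date returned about 1.0 and 3.0 in the same data. When all risk lay in the first 16 weeks, that crude before/after person-time ratio was itself about 0.1 under no effect, because the time after HSCT is mostly late, low-risk time. A Cox model on time since drug start compares patients at the same week and avoids this.

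**The case against.** The best defence is that the SAP claims little for this ratio. The section explores associated factors; SAP 4.1 makes all testing exploratory, with descriptive p-values and no preset significance level; SAP 4.2 has no decision rule; and Protocol 8.14 concedes that confounding may not be adequately handled. One factor in a list of 17 is affected. The order of events is largely reported elsewhere, so a careful reader could see how many cases under performed came before HSCT. The illustrative figures rest on inputs that no document gives. If risk is early, the longer window adds almost nothing. Whether VOD/SOS prevents a planned HSCT cannot be checked, because planned HSCT is not a collected variable.

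Most of this stands and limits the point. It does not rescue the ratio: exploratory status lowers the consequence but does not correct a comparison whose groups are defined partly by later events. The descriptive tables show the problem without supplying a usable comparison.

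SAP 8.2.3 could be read literally as counting, in recipients, only events after the last HSCT. The category for VOD/SOS before any HSCT and Protocol 8.8.14 show that earlier events are meant to count.

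**Conclusion.** The point holds for one exploratory risk ratio and its test. As specified, it cannot be interpreted even as an association of HSCT with later VOD/SOS, because it mixes event order, survival to HSCT and length of observation with any real association. That conclusion needs only the documents' definitions. The size does need assumptions: under no HSCT effect, illustrative ratios run from about 0.1 to 2.5 according to when VOD/SOS risk falls and whether VOD/SOS prevents HSCT.

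Four stronger readings are tempting and unsupported. A reader might infer that the ratio will be inflated; survival and the longer window push it up, but VOD/SOS followed by no HSCT pushes it down, and the documents do not settle the balance. A reader might infer that the SAP ignores event order; it does so only in this ratio and test. A reader might infer that the sample size or a main conclusion fails; neither depends on this ratio. Finally, a reader might expect the remedy to give the effect of HSCT; selection for transplant remains uncontrolled, so it too gives only an association.

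**What to change.** In SAP 8.2.3.1, for this factor only:

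1. Replace the ever/never risk ratio and test by a cause-specific Cox model for first VOD/SOS on time since drug start. HSCT is a time-dependent covariate: no until the first HSCT date after drug start, yes from then on. Follow-up ends at death or end of observation.
2. Label the result an exploratory association and state that selection for transplant is not controlled.
3. Keep the before/after counts in the performance-of-HSCT table as description. Do not add a crude before/after person-time ratio as a check unless it is split by time since drug start.
4. Extend the unequal-observation caution of SAP 8.2.4.4 and 8.2.4.5 to VOD/SOS.

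The cost is a paragraph of SAP text and one model. Dosing, HSCT, event and death dates are already collected (Protocol 8.8.3, 8.8.5, 8.8.12, 8.8.14). The downsides are few events (at the planning rate, 176 × 0.123 ≈ 22), hence a wide interval, and a hazard ratio that does not belong on the risk-ratio plot.
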